## 1. Study Summary

Study Title	Implementing and Evaluating the Effect of Personalized Pain Coaches After Orthopaedic Surgery for Patients with Sports Medicine Injuries to Improve Postoperative Outcomes
Study Design	Three arm randomized control trial
Primary Objective	The objective of this randomized controlled trial is to examine how the integration of a trained Life Care Specialist improves postoperative recovery related to patient-reported pain outcomes following orthopaedic injury
Secondary Objective(s)	Examine how the integration of a trained Life Care Specialist improves postoperative recovery related to opioid utilization and objective functional outcomes following orthopaedic injury
Research Intervention(s)/Interactions	The LCS will work with the patient to create a pain management plan focused on behavioral education. The LCS interventions can encompass all, but not limited to, the information included below: 

• Opioid Risk Education

• Therapeutic Intervention

• Clinical Pain Coordination

Study Population	Orthopaedic patients seen at Emory and Grady
Sample Size	150
Study Duration for individual participants	~90 days
Study Specific Abbreviations/ Definitions	LCS, Life care specialist
Funding Source (if any)	National Football League (NFL)

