## **6. Procedures Involved**

If the patient meets inclusion criteria, the CRC will visit patient during their preoperative consult or call the referred patient through his/her number listed on Epic. If unable to visit in person and reach through call, the CRC will message patient through the Secure Chat feature on Epic to potentially schedule an e-consent. If informed consent is obtained, they will be enrolled into REDCap for randomization into one of the three groups. A simple number generator, within RedCap, will sequentially randomize participants into control or one of the two intervention arms. After consenting, enrolling, and allocation, research staff will administer a battery of measures on tablets stored in REDCap, or on paper and later transcribed into REDCap to all participants. In the event the participant is unable to complete study measures during the clinic visit they will be emailed a secure link to RedCap to complete the consent form and the study measures.

Those randomized to the intervention will either meet with a Life Care Specialist for 1 hour before surgery, either in person or via Zoom® during their preoperative consult or at another time no later than 24 hours before surgery.

During their follow up visits with the surgical team at Grady Hospital or Emory Orthopaedics scheduled at 2-weeks, 6-weeks, and 3-months postoperatively participants will again be provided a tablet to complete outcome measures. In the event participants cannot physically travel to the clinic, appointments will be conducted over video conferencing and participants will have the option to be emailed the outcome measures to complete. If they are unable to complete the measures via email within 72-hours study staff will call participants to complete measures over the phone. If no response, paper copies of the measures will be mailed to participants with prepaid

**Protocol Title:** Implementing and Evaluating the Effect of Personalized Pain Coaches After Orthopaedic Surgery for Patients with Sports Medicine Injuries to Improve Postoperative Outcomes

---

postage to return them or QR code post cards to complete surveys. There is a one week window for the first follow up visit, two week window to complete measures for the second follow up study visit, and four weeks for the last study visit. Study staff will call participants and offer to video conference with them within 48 hours of surgery to review how to wear the actigraphy device and use the MEMS cap.

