#### **10. Inclusion and Exclusion Criteria**

We will recruit 150 participants from the orthopaedic sports medicine service at Grady and Emory Healthcare for this study. Individuals between 15–45 years old, scheduled for orthopaedic surgery due to sports medicine injuries (e.g., anterior cruciate ligament tears, meniscus injury, rotator cuff injury, etc.), and those who are actively employed or full-time athletes prior to injury will be eligible. Individuals unable to provide consent, those undergoing revision procedures, individuals without access to an internet connected device, and individuals who are unemployed or retired at time of injury will be ineligible. No one will be excluded from participation based on gender, race, or ethnicity. Individuals who are incarcerated or pregnant will not be eligible. Individuals unable to consent and those unable to communicate in English will be excluded since all surveys are validated in English.

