#### **19. Data Analysis, Management and Confidentiality**

**Protocol Title:** Implementing and Evaluating the Effect of Personalized Pain Coaches After Orthopaedic Surgery for Patients with Sports Medicine Injuries to Improve Postoperative Outcomes

---

Descriptive statistics will be used to examine the sample's characteristics and demographics (e.g., means, frequencies). Paired t-tests will be used to examine changes within participants from pre- to post-surgery. Mixed effects modeling will be used to examine mean change in outcomes over time and based on demographics as well as differences between those who do and do not work with the LCs while wearable devices are collecting data. Surveys will be coded with study participant ID numbers. All hard copies will be stored in locked filing cabinets in the PI's office. Paper survey data will be entered into RedCap. A master list of study ID # and names with emails of participants will be stored on Emory servers and only accessible to the PI and the coordinator.

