#### **25. Setting**

The study will take place across Grady and Emory Health's orthopaedic clinics.

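### Simple randomisation with no strata, and a model naming neither health system nor operated limb, gives up precision and interpretability that could be kept at little cost

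*Combined protocol and SAP*

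**What the plan says.** Section 1 calls the study a "Three arm randomized control trial". Section 6 says that after consent "they will be enrolled into REDCap for randomization into one of the three groups", and then: "A simple number generator, within RedCap, will sequentially randomize participants into control or one of the two intervention arms". That is the only account of how the sequence is generated. No ratio, block size, stratification factor or minimisation scheme appears anywhere.

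The population is mixed on two counts. Section 10 says "We will recruit 150 participants from the orthopaedic sports medicine service at Grady and Emory Healthcare for this study", and section 25 says "The study will take place across Grady and Emory Health's orthopaedic clinics". The eligible injuries in section 10 are an open-ended list covering knee and shoulder: "anterior cruciate ligament tears, meniscus injury, rotator cuff injury, etc".

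The whole analysis plan is a short paragraph in section 19. Besides descriptive statistics and paired t-tests, it says "Mixed effects modeling will be used to examine mean change in outcomes over time and based on demographics", together with differences by contact with the Life Care Specialist (LCS). The demographics listed in section 6 cover items such as date of birth, gender, ethnicity, body mass index, zip code and insurance. Hospital and operated region are not among them. The health-record items in section 6 include surgical time and regional anesthesia, but not procedure type, limb or site.

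**The concern.** The protocol's own choice of outcomes gives reason to expect these two factors to matter. Aim 2 rests on activity from a wrist-worn device, including daily steps. PROMIS Physical Function covers both the upper and the lower extremities. Knee and shoulder surgery could plausibly affect these measures differently. Health system may matter for opioid use, because the control arm's standard of care includes discharge instructions approved by the hospital system.

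With 150 patients in three arms, nothing in the described allocation prevents a chance excess of one limb or one hospital in one arm, and nothing in the model would correct for it. A reader of the results could not easily tell such an excess from an intervention effect. This includes Aim 3, which hopes to show that in-person and telehealth delivery give similar results. Even with perfect balance, leaving out a prognostic factor makes the estimates less precise.

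**Working it through.** **Inputs from the protocol.** N = 150 and three arms (sections 1 and 10); simple randomisation (section 6); PROMIS T-score SD of 10, a population norm (section 6).

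**Assumptions.** The protocol does not give the allocation ratio (1:1:1 assumed), the share of patients in the smaller limb or hospital group (q = 20%, 30% or 50%), the difference between limb groups (d = 3, 5 or 10 T-score points), or alpha and power (two-sided 5% and 80%, for illustration). No calculation is given for the 150, so that figure cannot be reproduced.

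**1. Arm sizes.** SD of one arm's size = √(150 × 1/3 × 2/3) = 5.8, with a 95% range of 39 to 61. In 400,000 simulated trials, the largest and smallest arms differ by 10 or more in 61% and by 15 or more in 31%. The smallest arm is 42 or fewer in 28%.

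**2. What unequal arms cost.** Power = Φ(δ / (10·√(1/n₁ + 1/n₂)) − 1.96), with δ set to give 80% at the expected sizes: 5.60 points for 50 v 50, and 4.85 for 100 v 50.

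| Comparison | Sizes | Power |
|---|---|---|
| Two arms | 45 v 55 | 79.6% |
| Two arms | 40 v 60 | 78.4% |
| Two arms | 40 v 55 | 76.9% |
| Pooled LCS v control | 110 v 40 | 74.8% |
| Pooled LCS v control | 90 v 60 | 82.9% |

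So the loss is 0.4 to 5.2 points in the unfavourable cases, and a large control arm gains power.

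**3. Chance imbalance in one binary factor (limb or hospital).** For pooled LCS v control, the SD of the difference in shares is about √(q(1−q)(1/100 + 1/50)). At q = 30% this is √(0.21 × 0.03) = 7.9 points. At q = 50% it is √(0.25 × 0.03) = 8.7 points. Simulation that also lets arm sizes vary gives:

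| q | Pooled LCS v control ≥10 points | Some pair of arms ≥15 points |
|---|---|---|
| 20% | 15% | 15% |
| 30% | 21% | 24% |
| 50% | 25% | 30% |

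For one pair named in advance, a gap of 15 points or more occurs in 6%, 11% and 14% of trials.

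**4. Shift in an unadjusted arm difference.** Shift = imbalance × d. For a 15-point imbalance: 0.15 × 3 = 0.45, 0.15 × 5 = 0.75 and 0.15 × 10 = 1.5 T-score points. For comparison, the standard error of a 50 v 50 difference is 10·√(2/50) = 2.0 points.

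**5. Precision lost by omitting limb, even with balance.** Variance explained R² = q(1−q)d²/100; the interval widens by 1/√(1−R²) − 1.

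| d | R² at q = 30%, 50% | Widening |
|---|---|---|
| 3 | 1.9%, 2.3% | about 1% |
| 5 | 5.3%, 6.3% | about 3% |
| 10 | 21%, 25% | 13%, 15% |

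**6. What stratified blocks would do.** Permuted blocks of 6 in four strata (health system by limb), 40,000 simulated trials: the mean gap between largest and smallest arm is about 2 patients, the 95th percentile 4 and the largest seen 8. The largest between-arm difference in limb share has a 95th percentile of 4.0 to 4.5 points, and no trial reached 10.

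**The case against.** - *Simple randomisation is valid.* This stands. A reader might infer that chance imbalance biases the trial or invalidates its test. It does not: the error rate of a randomised comparison already allows for it.
- *Unequal arms matter little.* This also stands. The 61% chance of a gap of 10 or more is striking, but step 2 shows a small cost and there is no bias.
- *No prognostic strength is documented.* Correct. It is tempting to call limb and hospital strong known predictors that move every outcome together. The documents give no such effects, and measures such as overdose knowledge or mindfulness have no stated reason to follow the operated limb. Hence the ranges for d; at 3 points the loss is slight.
- *The model already adjusts in part.* Surveys have a preoperative baseline and actigraphy a preoperative week, so modelling change removes some stable differences between groups. It does not remove postoperative effects specific to a procedure, and the listed demographics include neither factor.
- *Blocking or strata may exist in REDCap.* Possible, since the protocol is brief. The wording points to simple randomisation; if the system does something else, the protocol should say so.
- *Blocks make allocation easier to guess.* Fair, because in-person, Zoom and no-session arms are evident to staff. Varying, undisclosed block sizes limit this without removing it.
- *It may be too late to change the allocation.* Section 9 estimates enrolment to November 2023. The revision of 02/01/2024 still adds a recruitment contact method, so some enrolment probably remained, but the number is unknown. Covariate adjustment is therefore the main remedy.

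**Conclusion.** The point holds as an avoidable loss of precision and interpretability, not as a flaw in the trial's validity. Under 1:1:1 allocation and a 30% to 50% share, roughly one trial in four or five would show an imbalance of 10 or more percentage points between pooled LCS and control on a given factor. About 24% to 30% would show 15 or more points between some pair of arms. Whether that matters depends on the difference between limb groups, which the documents do not give. At 3 points the effect is minor. At 10 points, a 15-point imbalance moves an unadjusted difference by 1.5 points, three-quarters of its standard error (1.5/2.0), and omitting limb widens intervals by 13% to 15%. These precision figures take the normative SD of 10 as the outcome SD; a model of change from baseline could have a different residual SD.

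A reader might also assume that adjustment needs only data already in hand. The documents do not show this, because section 6 lists neither limb, procedure nor site among the items collected.

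**What to change.** 1. Add operated region (upper or lower limb) and health system (Grady or Emory) to the data collected in section 6, for every participant including those already randomised. Both should be abstractable from the health records the study already uses.
2. In section 19, prespecify both as fixed effects in every arm comparison, before outcomes are examined by arm.
3. In section 6, state the allocation ratio. For anyone still to be randomised, load a REDCap allocation table of permuted blocks of varying size (for example 3 and 6), stratified by health system and upper or lower limb. Keep block sizes concealed from staff who enrol.

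The cost is two abstracted fields, one sentence in the analysis section and, if enrolment is open, one new allocation table. The downside is somewhat more predictable allocation near block ends where staff know the arms, limited by the concealed, varying sizes. If enrolment has closed, items 1 and 2 still apply.

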#### **4. Study Endpoints**

During the conduct of this study, assessments will occur one month to one week prior to surgery, 2 weeks, 6 weeks, and 3 months postoperatively. Study measures at these points will assess patient-reported outcomes using surveys, opioid consumption using both electronic health records and remote monitoring, and functioning using wearable actigraphy devices.

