## **9. Study Timelines**

Study will commence upon IRB approval. Individuals undergoing surgery will be referred by their surgeon to the team who will then contact them to screen for eligibility and interest in enrolling. Study staff will meet with participants during their preoperative visit or over zoom to administer baseline surveys. Those randomized to the intervention arms will also meet with the study intervention team member during that visit. Study staff will meet with participants at each of their postoperative visits, 2 weeks, 6 weeks,

and 3 months. Participants will be discharged from the study at 3 months. Enrollment will continue for 1 year after the start of the study (estimated November 2022–November 2023), data collection will be completed 6 months after (estimated May 2024). Data analyses will be completed by November 2024. Study duration for participants is approximately 90 days.

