#### **14. Recruitment Methods**

Potential patient participants will be identified during the daily orthopaedic morning report by surgeons and their staff. Additionally, flyers with study information and brief videos on study will be placed in the clinic waiting room areas and provided to potential participants from their surgical teams to contact the study team and let them know study staff may contact them. The CRC will visit patient during their preoperative consult or call the referred patient through his/her number listed on Epic. If unable to visit in person and reach through call, the CRC will message patient through the Secure Chat feature on Epic (MyChart) to potentially schedule an appointment to review eligibility, provide e-consent, and complete study baseline activities before surgery. A member of the research team will conduct the informed consent discussion with patients and will obtain consent using the IRB-approved consent form either in person or through e-consent in RedCap.

If the patient is a minor, the research team member will conduct the informed consent discussion with both the patient and at least one of the parents/legal guardians, and obtain the patient's assent with parental permission using the IRB-approved consent form. This can also be done in person or through e-consent in RedCap.

Informed voluntary consent will be obtained from each subject in a non-coercive manner.

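### The baseline battery is given after allocation and is not tied to the LCS session, so comparisons of change in patient-reported outcomes between arms can be biased

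*Combined protocol and SAP*

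**What the plan says.** Section 6 (Procedures Involved) randomises in REDCap once consent is given, and then: "After consenting, enrolling, and allocation, research staff will administer a battery of measures on tablets stored in REDCap". Late completion is allowed: "In the event the participant is unable to complete study measures during the clinic visit they will be emailed a secure link to RedCap". That link is described as serving "to complete the consent form and the study measures".

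The LCS session is held "during their preoperative consult or at another time no later than 24 hours before surgery" (Section 6). Section 9 (Study Timelines) has staff give the baseline surveys at the preoperative visit or over Zoom, and adds: "Those randomized to the intervention arms will also meet with the study intervention team member during that visit". It does not fix the order of surveys and session within the visit.

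Two limits on baseline timing are stated. Section 4 says that "assessments will occur one month to one week prior to surgery". Section 14, for patients reached by secure message, says they are to "provide e-consent, and complete study baseline activities before surgery". Both are relative to surgery; neither refers to allocation or to the LCS session.

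Section 5 contains one ordering rule. In the LCS arms the Opioid Risk Tool, the substance abuse survey and the mental health screening come before the opioid education. The control arm receives usual care only. Blinding is not mentioned in any section.

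Section 19 plans paired t-tests from before to after surgery and mixed models of mean change over time. It does not say how the baseline enters the comparison between arms.

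**The concern.** A baseline value protects a randomised comparison only if allocation cannot influence it. Here most of the battery is self-reported: PROMIS pain interference, sleep disturbance, physical function and medication misuse, the mindfulness scale (MAAS) and naloxone knowledge. A participant who has just learned the arm may answer differently. One who has already had the LCS hour may answer differently because of the intervention itself.

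The naloxone questionnaire and the MAAS are the clearest cases. The session includes naloxone education and the Community Resiliency Model, which Section 5 presents as a form of mindfulness.

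Patient-reported pain is the primary objective (Section 1). If the pre-surgery values differ by arm because of allocation, an analysis of change carries that difference into the estimated effect. The error can go either way. A benefit already visible at baseline shrinks the estimated effect; worse reporting at baseline in the LCS arms inflates it.

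**Working it through.** **Order of events.** Setting the sections side by side:

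- Section 6 puts allocation before the battery.
- Under the Section 4 window, a session at a consult one month before surgery, with the battery finished by link one week before surgery, puts the baseline about three weeks after the session (30 − 7 = 23 days).
- Under the same rules, a battery one week before surgery and a session 24 hours before surgery puts the baseline six days ahead of the session (7 − 1 = 6), though still after allocation.
- The Section 5 rule covers the Opioid Risk Tool, the substance abuse survey and the mental health screening, relative to opioid education only. It does not cover PROMIS, MAAS or the naloxone questionnaire.
- The emailed link bundles the consent form with the measures. On that route some measures might come before allocation, which conflicts with the order stated just before it.

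**Size.** The plan gives no power calculation, effect size or trial SD, so there is no planned figure to reproduce. The following is an illustration.

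Inputs from the documents: 150 participants (Sections 1, 10 and 13); SD 10 T-score points, the US norm for PROMIS measures (Section 6). Assumptions: 50 per arm, so 100 LCS v 50 control; two-sided 5% level; pre-post correlation ρ of 0.3 to 0.7; a shift of b points in the LCS arms' baseline mean caused by allocation or the session; no true effect at follow-up.

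If the LCS baseline mean moves by −b, the expected estimates are:

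- change score, or arm-by-time contrast with free baseline means: 0 − (−b) = b
- ANCOVA, where the within-arm slope is ρ because both SDs are equal: 0 − ρ(−b) = ρb
- follow-up only: 0

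The standard error is s × √(1/100 + 1/50) = 0.1732s, with s = 10√(2(1 − ρ)) for change, 10√(1 − ρ²) for ANCOVA and 10 for follow-up only. By normal approximation:

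| ρ | b | Change: bias | Change: rejection rate | ANCOVA: bias | ANCOVA: rejection rate |
|---|---|---|---|---|---|
| 0.3 | 1 | 1.0 | 0.08 | 0.3 | 0.05 |
| 0.3 | 2 | 2.0 | 0.16 | 0.6 | 0.07 |
| 0.5 | 1 | 1.0 | 0.09 | 0.5 | 0.06 |
| 0.5 | 2 | 2.0 | 0.21 | 1.0 | 0.10 |
| 0.7 | 1 | 1.0 | 0.12 | 0.7 | 0.09 |
| 0.7 | 2 | 2.0 | 0.32 | 1.4 | 0.21 |

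Follow-up only has bias 0 and rejection rate 0.05 throughout. A simulation of 4,000 trials at b = 3, ρ = 0.5 gave mean biases of 3.00 (change), 1.50 (ANCOVA) and 0.00 (follow-up only), as the formulas predict.

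**For scale.** The difference detectable with 80% power at follow-up is 0.1732 × 10 × (1.960 + 0.842) = 4.9 points. A 2-point change-score bias is 2/4.85 = 41% of it. The ANCOVA range of 0.3 to 1.0 points (ρ 0.3 to 0.5) is 6% to 21% of it.

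**The same shift hiding a benefit.** With a true 5-point benefit, b = 3 and ρ = 0.5, the change analysis shows 5 − 3 = 2 points and has power 0.21. The follow-up-only comparison has power 0.82.

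**The case against.** The strongest reply is that the plan permits contamination rather than schedules it, and that several features limit it.

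- **Timing.** A reader of Section 14 might infer that surgery is the only limit on baseline completion. It is not: Section 4 ends the window one week before surgery, while the session may be as late as 24 hours before. A baseline can therefore precede the session by days. This stands, but it does not put the baseline before allocation, and nothing requires that sequence.
- **Protected items.** The Section 5 rule covers the Opioid Risk Tool, substance abuse and mental health items relative to opioid education. This stands for those items only.
- **Knowledge of arm.** Section 6 gives the time of allocation, not of disclosure. That participants know their arm is an inference, though a strong one, since the control arm has no counterpart to the LCS session.
- **Recall.** PROMIS sleep disturbance and pain interference ask about the past seven days, which limits what a same-day session can move. It does not limit the MAAS or naloxone knowledge in the same way.
- **Analysis.** The paired t-tests are within participants and are not the treatment contrast, and the mixed model leaves baseline handling open. So it is not true that every baseline shift must reach the treatment effect. But the plan does not commit to an analysis that would be immune.
- **Outcomes and contrasts outside the problem.** Opioid doses from the health record and inpatient pain ratings do not use the battery. In the in-person v virtual comparison (Aim 3), a shift common to both LCS arms cancels.
- **Dropout.** One might infer that disappointed control participants leave before giving a baseline. The documents offer no evidence of this, and Section 18 pays for finishing the baseline visit.

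**Conclusion.** The concern holds as a design weakness: allocation precedes the battery, and nothing ties PROMIS, MAAS or the naloxone questionnaire to a time before disclosure or before the session. Contrasts between arms in change on these measures can be biased.

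The documents do not support the stronger reading that the baselines are contaminated and the effect is biased. They contain nothing from which the size or direction of a shift could be derived, and the bias depends on an estimator that Section 19 leaves open. The 1 to 2 points used here are an assumption. They translate into 1 to 2 points for change scores, 0.3 to 1.0 points for ANCOVA at ρ of 0.3 to 0.5, and nothing for follow-up only, against about 4.9 points detectable. That last figure assumes equal arms, SD 10 and no dropout. Confidence is high on the ordering and low on the magnitude.

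**What to change.** **For new participants.** Reorder Section 6 to consent, complete the baseline battery, then randomise. Have REDCap withhold the allocation until the battery is complete, including on the e-consent and emailed routes. Record the completion date and time on paper forms, because REDCap would time only the transcription. Reconcile the emailed-link sentence and the timing statements in Sections 4, 9 and 14 with this order. With the battery completed before allocation, b is 0 by design for the surveys.

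**For participants already enrolled.** These may be the majority, since the revision history runs to February 2024 and Section 9 estimated that enrolment would end in November 2023. Record the times of allocation, battery and LCS session. Simply dropping post-allocation baselines would not work: under the stated order that is nearly all of them, and no baseline-based analysis would remain. Instead add a sensitivity analysis that uses no post-allocation baseline: either follow-up only, or adjusted only for variables fixed before allocation, such as age or pre-existing conditions from the record.

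**Actigraphy.** Reordering the surveys does not help the device baseline. It is worn in the week before hospitalisation (Section 6), which can overlap or follow the LCS session. Section 19 should not treat that week as an uncontaminated baseline.

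**Cost.** A REDCap setting and edits to four sections; some participants are randomised slightly later. The sample size does not change. The follow-up-only sensitivity analysis gives up some precision: at ρ = 0.5 its standard error is 1.73 points, against 0.1732 × 8.66 = 1.50 for ANCOVA.
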